### **I. Potentially effective antibiotics use**

Potentially effective antibiotics, for the purpose of this SAP, include metronidazole and ciprofloxacin, which may impact the subject's perianal fistulizing CD when administered as following for the indication of perianal fistulizing CD or CD:

- Commencement of a new antibiotics use after the first dosing date of study drug for 7 or more days;
- Escalation of the dose of antibiotics above the baseline dose for 7 or more days.

## **II. Potentially effective immunomodulator use**

### **Commencement of a different class of oral, IM, SC, or IV immunomodulator drugs**

(where the subject was not previously taking concomitant immunomodulators of the same class on Day 1), including but not limited to 6-MP, azathioprine, MTX, 6-thioguanine, and prohibited immunomodulators including but not limited to cyclosporine, leflunomide, tacrolimus, thalidomide regardless of dose, for 7 continuous days. The use of an immunomodulator will be considered potentially effective when it is administered for the indication of perianal fistulizing CD or CD.

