 - i) Active disease despite a history of at least a 12-week regimen of oral azathioprine (≥ 2 mg/kg) or 6-mercaptopurine (6-MP) (≥ 1 mg/kg), or methotrexate (25 mg per week subcutaneously [SC] or intramuscularly [IM] per week for induction and ≥ 15 mg IM per week for maintenance), OR
 - ii) History of intolerance to at least one immunomodulator including, but not limited to, serious infections, hepatotoxicity, cytopenia, pancreatitis, TPMT genetic mutation, allergic reactions, or any other condition that contributed to discontinuation of the agent

AND/OR

- c) TNF α Antagonist
 - i) Active disease despite a history of at least one induction regimen of infliximab, adalimumab, certolizumab or biosimilar as follows:
 - (1) Infliximab: A 14-week induction regimen of 5 mg/kg IV at Weeks 0, 2, and 6 (6 week induction regimen with 2 doses at Weeks 0 and 2 in EU)
 - (2) Adalimumab: A 4-week induction regimen consisting of 160 mg SC (four 40-mg injections in 1 day or two 40-mg injections per day for 2 consecutive days) on Day 1, followed by a second dose 2 weeks later (Day 15) of 80 mg.
 - (3) Certolizumab: A 8-week induction regimen of 400 mg SC at Weeks 0, 2, and 4

AND/OR

- ii) Recurrence of symptoms during maintenance therapy with the above agents,

AND/OR

- iii) History of intolerance to any TNF α inhibitors including, but not limited to, serious infections, hepatotoxicity, heart failure, allergic reactions, or any other condition that contributed to discontinuation of the agent

- 9) Is willing and able to undergo MRI per protocol requirements
- 10) Is willing and able to undergo flexible sigmoidoscopy per protocol requirements
- 11) Meet one of the following tuberculosis (TB) screening criteria:
 - a) No evidence of active or latent TB ie,
 - i) A negative QuantiFERON® TB-Gold In-Tube test at screening, AND
 - ii) A chest radiograph (views as per local guidelines) taken at screening or within the 3 months prior to screening (with the report or films available for investigator review) without evidence of active or latent TB infection, AND
 - iii) No history of either untreated or inadequately treated latent or active TB infection

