- a) Oral 5-aminosalicylate (5-ASA) compounds provided the dose prescribed has been stable for at least 4 weeks prior to randomization; dose must remain stable for the first 10 weeks after randomization
- b) Oral corticosteroid therapy (prednisone prescribed at a stable dose $\leq 20 \text{ mg/day}$ or budesonide prescribed at a dose of $\leq 6 \text{ mg/day}$) provided the dose prescribed has been stable for 4 weeks prior to randomization; dose must remain stable for the first 10 weeks after randomization
- c) Azathioprine or 6-MP or methotrexate provided the dose prescribed has been stable for 4 weeks prior to randomization; dose must remain stable for the first 10 weeks after randomization
- d) Antibiotics for the treatment of perianal fistulizing CD (eg, metronidazole, ciprofloxacin) provided the dose prescribed has been stable for the 2 weeks prior to randomization. Dose must remain stable for the first 10 weeks after randomization. Subjects who are on cyclic therapy must continue their standard low-dose regimen without change for the first 10 weeks after randomization.
- e) Vedolizumab therapy (300 mg IV) for the treatment of concurrent luminal disease activity provided the dose has been stable for 14 weeks prior to randomization; subjects must remain on vedolizumab for the duration of their participation in the study. Subjects on concurrent vedolizumab therapy must not be taking concurrent azathioprine or 6-MP or methotrexate.

14) Willingness to refrain from live or attenuated vaccines during the study and for 12 weeks after last dose of study drug

15) Must be up to date on colorectal cancer screening and surveillance as standard of care according to local guidelines.

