5.4.1. Allowed Concomitant Medication

The allowed concomitant medication(s) for CD must be maintained at a stable dose for the noted time without dose alteration or discontinuation. Subjects should not initiate new induction therapy prior to the screening visit. If a new therapy has been recently initiated, the full induction course should be completed prior to screening consideration.

The allowed medications for CD are as follows:

- Oral 5-ASA compounds provided the dose prescribed has been stable for at least 4 weeks prior to randomization; dose must be stable for the first 10 weeks after randomization
- Azathioprine, 6-MP, or MTX provided the dose prescribed has been stable for 4 weeks prior to randomization; dose must be stable for the first 10 weeks after randomization
- Oral corticosteroid therapy (prednisone prescribed at a stable dose of \leq 20 mg/day or budesonide prescribed at a stable dose of \leq 6 mg/day) provided the dose prescribed has been stable for 4 weeks prior to randomization; dose must be stable for the first 10 weeks after randomization.
- Antidiarrheals for chronic diarrhea are allowed throughout the study as necessary for control of chronic diarrhea; stable doses are encouraged.
- Occasional use of non-steroidal anti-inflammatory drugs (NSAIDs) for transient symptoms is permitted; daily use of aspirin up to 162.5 mg for the purpose of cardiovascular prophylaxis is permitted.
- Antibiotics for the treatment of perianal fistulizing CD (eg, metronidazole, ciprofloxacin) provided the dose prescribed has been stable for the 2 weeks prior to randomization. Dose must remain stable for the first 10 weeks after randomization. Subjects who are on cyclic therapy must continue their standard low-dose regimen without change for the first 10 weeks after randomization
- Vedolizumab therapy (300 mg IV) for the treatment of concurrent luminal disease activity provided the dose has been stable for 14 weeks prior to randomization; subjects must remain on vedolizumab for the duration of their participation in the study. Subjects on concurrent vedolizumab therapy must not be taking concurrent azathioprine or 6-MP or methotrexate.

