6. STUDY PROCEDURES

The study procedures to be conducted for each subject enrolled in the study are detailed in tabular form in [Appendix 2](#). Key procedures are described in the text that follows.

Written informed consent must be obtained from each subject before initiation of any screening procedure. **CCI**

From the time of obtaining informed consent through the Week 10 visit, subjects must maintain allowed concomitant medications at a stable dose (see Section [5.4.1](#)).

The investigator must document any deviation from protocol procedures and notify the Sponsor or contract research organization.

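### Raising an immunomodulator dose between Week 10 and Week 24 is permitted and is not a treatment failure, although raising an antibiotic dose under the same stability rule is

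*SAP*

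**What the plan says.** Protocol section 4.2, criterion 13c, allows "Azathioprine or 6-MP or methotrexate provided the dose prescribed has been stable for 4 weeks prior to randomization" and adds: "dose must remain stable for the first 10 weeks after randomization". Section 5.4.1 repeats this. Section 6 sets the general duty: "From the time of obtaining informed consent through the Week 10 visit, subjects must maintain allowed concomitant medications at a stable dose". Table 5-1 does not list these three drugs as prohibited, and no other section restricts their dose after Week 10. Where the protocol wanted cover for the whole study it said so; for vedolizumab, "subjects must remain on vedolizumab for the duration of their participation in the study".

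SAP Appendix 11 governs combined fistula response, combined fistula remission and the two time-to-event endpoints. Its immunomodulator rule (II) is triggered by starting a different class, in the situation "where the subject was not previously taking concomitant immunomodulators of the same class on Day 1". Appendix 10 II, which governs Week 24 proctitis remission, has the same trigger. The antibiotic rule in Appendix 11 I has a second limb: "Escalation of the dose of antibiotics above the baseline dose for 7 or more days". Appendix 10 I has a comparable escalation limb for steroids.

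**The concern.** The SAP calls immunomodulators potentially effective for the disease under study and discards efficacy data after a new class is started. A dose increase in a class already taken is also an intensification of background therapy, yet it has no analytic consequence. If fistula drainage stops after such an increase, the response counts for the randomised arm.

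The results exposed are the primary endpoint, combined remission, proctitis remission, and any clinical response or remission first seen after the increase in the time-to-event analyses. No hypothesis test is planned, so the estimated difference and its 90% interval are the main result. With 15 placebo subjects, one or two reclassified responders are visible in that estimate.

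**Working it through.** **1. The rules side by side**

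| Drug group | Protocol dose rule | Failure trigger, fistula endpoints (App. 11) | Failure trigger, luminal endpoints (App. 10) |
|---|---|---|---|
| Immunomodulators | Stable to Week 10, then no rule | New class only | New class only |
| Antibiotics for fistulae | Stable to Week 10, then no rule | New use or escalation | No rule |
| Steroids | Stable to Week 10, then taper | No rule | New use or escalation |
| Biologics | Vedolizumab kept throughout; TNF antagonists, natalizumab and ustekinumab prohibited | Start only | Start only |

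The first two rows share a dose rule but differ in trigger. Appendix 11 II's reference to any dose describes a newly started drug, and its open-ended list widens the drugs covered, not the event that triggers failure. Non-responder imputation (SAP section 6.1) acts only when measurements are insufficient, so an escalated subject with Week 24 data is scored as observed. An increase before Week 10 would breach the protocol but would not be a failure either.

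**2. Length of the open period**

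24 − 10 = 14 weeks; by study day, (169 − 71)/7 = 14.0 weeks. That is 14/24 = 58% of the treatment period.

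**3. The plan's own precision figures**

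SAP Table 1-1 (n = 30, exact 90% interval) uses lower limit = Beta quantile(0.05; x, n − x + 1) and upper limit = Beta quantile(0.95; x + 1, n − x). All 14 limits reproduce after rounding; for example 12/30 gives 24.95% to 56.61%, against the printed 25% and 57%. The gap leaves this table unchanged.

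**4. Weight of one responder**

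Planned arms are 30, 30 and 15. Placebo: 1/15 = 6.7 points. Filgotinib arm: 1/30 = 3.3 points.

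**5. Illustration (counts assumed)**

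Take 12/30 on one filgotinib dose and 3/15 on placebo, and suppose the added rule turns some counted responders into non-responders. The SAP names no interval method for the difference; a Wald 90% interval is assumed, d ± 1.645 × √[p₁(1 − p₁)/30 + p₀(1 − p₀)/15].

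| Reclassified | Difference (points) | 90% interval |
|---|---|---|
| None | 20.0 | −2.5 to 42.5 |
| 1 filgotinib | 16.7 | −5.6 to 39.0 |
| 2 filgotinib | 13.3 | −8.8 to 35.4 |
| 1 placebo | 26.7 | 6.1 to 47.3 |
| 2 filgotinib and 1 placebo | 20.0 | −0.2 to 40.2 |

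**6. How many such subjects (all inputs assumed)**

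Let u = share on an immunomodulator at Day 1 (20–40%), e = share of those escalated (10–30%), r = share of those counted as responders (20–40%). The expected number is n·u·e·r.

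- Filgotinib arm: 30 × 0.2 × 0.1 × 0.2 = 0.12, up to 30 × 0.4 × 0.3 × 0.4 = 1.44.
- Placebo: half of these, 0.06 to 0.72.
- Chance of at least one, 1 − (1 − uer)ⁿ: 11–77% per filgotinib arm and 6–52% in placebo.
- Chance of two or more in placebo, with p = uer from 0.004 to 0.048, 1 − (1 − p)¹⁵ − 15p(1 − p)¹⁴: about 0.2% to 16%.

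**The case against.** The strongest reply is that few subjects are exposed. A new start or new class is already caught. Criterion 13e bars these drugs alongside vedolizumab. Week 10 non-responders and later luminal worseners must leave blinded treatment (protocol sections 3.4 and 3.6 to 3.8). The trial is descriptive, and its interval is already 45 points wide in the illustration. This stands as a limit on size. It does not close the gap: the perianal exit rule requires a worse PDAI subscore at Weeks 6 and 10, so a subject whose fistula still drains but is no worse can stay and be escalated.

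Leaving a permitted change as observed is also a legitimate choice of estimand. The SAP does not state that choice, and it sits awkwardly with Appendix 11, which sets data to missing after failure and counts escalation of another permitted drug.

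Four stronger readings are tempting but unsupported.

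- *Immunomodulators alone lack an escalation rule.* Appendix 11 has no steroid rule, and both biologic rules are start-only. For fistula endpoints the comparison rests on antibiotics.
- *Fourteen weeks is shown to be long enough for an increase to act.* Criterion 8b ("Active disease despite a history of at least a 12-week regimen of oral azathioprine") defines inadequate response to a regimen at a stated minimum dose, not the time an increase needs. The Week 24 MRI may also be done up to 14 days early.
- *The bias runs toward zero.* That needs escalation to cluster in placebo, which nothing in the documents shows. Escalation in a filgotinib arm inflates the difference.
- *The effect is large.* With assumed counts of 15/30 and 3/15, two extra placebo responders would cut 30 points to 15/30 − 5/15 = 16.7, and three to 10. Under the ranges above, two or more has at most about a 16% chance and three or more about 3%, including subjects who would have responded anyway.

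**Conclusion.** The gap and the inconsistency with the antibiotic rule are clear from the text. A Day 1 user of azathioprine, 6-MP or methotrexate, not on vedolizumab and still on blinded treatment after Week 10, can have the dose raised within protocol and count as a responder. The steroid limb in Appendix 10 I shows the same inconsistency for the luminal endpoints, including proctitis remission.

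Neither the direction nor the size of the bias can be established, since the numbers of users and escalations are not in the documents. Under the assumed ranges, zero or one affected placebo responder is the usual case. Type I error and power are not at issue. The point concerns what the estimated difference measures, and it merits a short SAP change.

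**What to change.** Before unblinding:

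- Add to Appendix 11 II and Appendix 10 II that escalation of a concomitant immunomodulator above the Day 1 dose, for the indication each appendix already states, is a treatment failure.
- Word the duration so that it works for weekly methotrexate; a count of continuous days fits a weekly drug poorly.
- Define class, for example azathioprine and 6-MP as one class with a stated conversion, so that a switch within class is handled predictably.
- Report escalation counts by arm, and a sensitivity analysis with these subjects scored as observed.

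If the as-observed handling was intended, the SAP should say so and report the failure handling as the sensitivity analysis.

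The cost is a few sentences and one extra analysis, with no change to patient care. A few more subjects will be scored as non-responders, and time-to-event data after an escalation will be censored. Data availability needs checking: protocol section 5.4 puts concomitant medications on the eCRF, but section 9.1.5 lists dose and dose changes only among source data.

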## **III. Potentially effective biologic agent use**

**Commencement of a biologic agent** including TNF $\alpha$  antagonists, regardless of indication for use and duration ([Appendix 2](#)).

## **Appendix 12. Determining Missing and Virtual Visits due to COVID-19**

This appendix describes the clinical trial site collection of COVID-19 data pertaining to missed/virtual visits and the data processing algorithm used to determine which visits were missing and which visits were virtual.

### Data collection

A COVID-19 supplement to the eCRF Completion Guidelines was provided by data management to instruct clinical trial sites with respect to data entry expectations pertaining to scenarios related to the COVID-19 pandemic. If a visit was missed, sites should enter “Visit missed due to COVID-19.” If an in-person visit was conducted virtually, sites should enter “Virtual visit due to COVID-19.”

### Determination of Missed and Virtual visits

Natural Language Processing (NLP) was used to search the CRF comment fields to identify instances of “COVID-19” (or synonyms, see [Table 13-6](#)) and “Virtual” (or synonyms, see [Table 13-6](#)). The search terms are maintained in a global lookup table and can be modified to tune the NLP model. For any comments with COVID-19 search terms, assign “Missed Visit” or “Virtual Visit” as follows:

- i) If COVID-19 terms are identified through NLP and the visit date is missing, then result is “Missed Visit”
- ii) If COVID-19 and Virtual terms are identified through NLP for a visit, then result is “Virtual Visit”. When there are multiple records for the same subject and the same visit, NLP will be based on multiple records to ensure 1 unique category per subject per visit
- iii) Otherwise result is missing

**Table 13-6. Examples of Search Terms for “COVID-19” and “Virtual” Used to Identify Missed and Virtual Visits**

Search terms for “COVID-19”	Search terms for “Virtual”
COVID19	VIRTUAL
CORONA	TELEMED
CORONAVIRUS	TELEHEALTH
PANDEMIC	TELEPHONE
OUTBREAK	REMOTE
CRISIS	TELEMEDICINE
LOCKDOWN	TELECONSULTATION
QUARANTINE	TELEPHONICALLY
SHELTER	PHONE
	HOME VISIT
	ZOOM
	SKYPE

